### **3.2. Modified Rankin Score (mRS)**

The mRS is a 7-point scale, ranging from 0 (normal) to 6 (dead), where at baseline the scores were from 0 to 5 (discharged dead were excluded from the study). During follow-up, patients were scored a 6 at the 3, 6 and 12-month follow-up if the patient died before the respective follow-up (even if the patient missed intervening visits). The mRS will be dichotomized as “good outcomes” of 0 to 2 points, and “poor outcomes” of 3 to 6 points. Analysis will use a mixed model approach (implemented through GLIMMIX) with the treatment-specific proportion of “good outcomes” modeled at months 0, 3, 6, and 12 (reported with the p-value for treatment differences at each time point). The primary outcome will be treatment differences in the change in the proportion with good outcomes between months 0 and 12, but differences to months 3 and 6 will also be estimated. These differences will be estimated with the same 4-level incremental adjustments, and with both unadjusted and inverse-probability weighted adjustment. Effect modification will be assessed by age, sex, race/ethnicity, stroke sub-type, stroke severity (discharge NIHSS dichotomized at 0 to 1 versus 2+), and nSES. With the discharge mRS as an outcome, the analysis will not be adjusted for baseline mRS.

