Once consented, study personnel will obtain the location to which the patient will be discharged, and baseline assessments will be obtained. In addition, to data collected from the patient, the patient's caregiver and other contacts will be identified and collected to ensure recontact for future research visits and study goals and schedule will be reviewed. Informed

consent will be obtained from both the patient and the caregiver or their legal surrogate prior to data collection.

Participant Retention.

Monitoring of potential patient dropout and loss to follow up at each clinical site will be conducted at an early stage (in-person, by phone, or virtually using the Vivify Health Go App, Samsung Tablet, or other audio/video capabilities) to allow intervention. Both will be mitigated by having C3FIT's site personnel encourage and maintain participation and patient engagement, providing monthly feedback reports, having the

Clinical Site PI contact patients/caregivers to discuss feelings about continuing participation, and utilizing other techniques identified in our demonstration project. Data from monitoring visits, GWTG, and the SDCC will be used by the CCC to monitor fidelity of the intervention during the period of enrollment and follow-up.

[figure not shown]
Participant Reimbursement. Research participants can be reimbursed for their time and effort on C3FIT at a rate of \$25 for the collection of study outcomes at baseline, 3, 6, and 12 months by completing a SRU call and an intervention research visit for a total of \$100. For each follow up intervention research visit (1,2,4,5,7,8,9,10,11 months) the participant will receive \$20 which equals \$180. Compensation will be provided in a method in alignment with each sites' institutional policies.

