Participant Retention. Monitoring of potential patient dropout and loss to follow up at each clinical site will be conducted at an early stage (in-person, by phone, or virtually using the Vivify Go App or other audio/video capabilities) to allow intervention. Both will be mitigated by having C3FIT's site personnel encourage and maintain participation and patient engagement, providing monthly feedback reports, having the Clinical Site PI contact patients/caregivers to discuss feelings about continuing participation, and utilizing other techniques identified in our demonstration project. Data from monitoring visits, GWTG, and the SDCC will be used by the CCC to monitor fidelity of the intervention during the period of enrollment and follow-up.

Participant Reimbursement. Research participants can be reimbursed for their time and effort in C3FIT at a rate of \$25 for the collection of study outcomes at baseline, 3, 6, and 12 months by completing a SRU call and an intervention research visit for a total of \$100. Sites that elect to provide reimbursement will do so in a method in alignment with their own site's institutional policies.

Figure 4. C3FIT Patient Flow Diagram – CSC/PSC Arm Only

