In addition to this primary analysis of the intermediate factors that is restricted to those not compliant/adherent at discharge, a supplemental analysis will assess the proportion compliant at 3, 6, and 12 months regardless of compliance at month 0 (i.e., proportion compliant/adherent in the entire population). This analysis will consider a mixed modeling approach with outcomes at 4 time points (0, 3, 6, and 12 months). The focus of this analysis will be on the change in the proportion compliant between month 0 and 12 months (but also reporting the change in the proportion to 3 and 6 months). In addition to assessing treatment differences in the change in the proportion, the treatment differences in the proportions at the 4 time points will be assessed.

For all six factors, analyses assessing the potential for bias from missingness will be performed using inverse probability weighting (for both the analysis restricted to those not compliant/adherent and for the entire population analysis). This will be conducted by first developing a logistic regression model estimated in all subjects predicting the probability of observing the 12-month observation. Predictors in the model will be site (with cluster randomization, implicitly including treatment effect), age, NHW race/ethnicity, sex, NIHSS and nSES. The inverse of this probability will be standardized by dividing by the sum of the inverses, standardizing the inverse probabilities to have the same sum as the sample size; hence, not inflating or deflating statistical power. The analysis for the factor will then be repeated using the inverse probability weights. Should the interpretation of results differ between the weighted and unweighted analyses, the primary interpretation will be based on the weighted analysis, and the weighted analysis will be the basis for figures and estimates in the manuscript will focus on the weighted results.

Effect modification will be assessed by age, sex, race/ethnicity, stroke sub-type, stroke severity (discharge NIHSS dichotomized at 0 to 1 versus 2+), and nSES.

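### On the mRS a known death always has a 12-month value but a survivor may not, and the inverse-probability weights ignore vital status, so they do not correct the imbalance

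*SAP*

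**What the plan says.** SAP 3.2 dichotomises the mRS at 0 to 2 versus 3 to 6. For deaths, "patients were scored a 6 at the 3, 6 and 12-month follow-up if the patient died before the respective follow-up", and this applies "even if the patient missed intervening visits". No score is specified for a living patient without an mRS. The primary contrast is "treatment differences in the change in the proportion with good outcomes between months 0 and 12". Patients who died before discharge are excluded, so month 0 contains no deaths. Estimates are produced "with both unadjusted and inverse-probability weighted adjustment".

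The weighting method is in SAP 3.1: a "logistic regression model estimated in all subjects predicting the probability of observing the 12-month observation". Its predictors are site, age, race/ethnicity, sex, NIHSS and nSES. Vital status is not among them, and the SAP does not say whether a death counts as observed in this model.

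In both arms' protocols (Table 7) the smRS at months 3, 6 and 12 is collected by the telephone survey unit. Mortality is tracked separately through site contact: monthly in ISPU, and at months 3, 6 and 12 in CSC/PSC.

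Contact and payment also differ (section 4.F, Participant Reimbursement). In ISPU, "For each follow up intervention research visit (1,2,4,5,7,8,9,10,11 months) the participant will receive" a separate payment, in addition to the payment for outcome collection. In CSC/PSC, "Sites that elect to provide reimbursement will do so in a method in alignment with their own site's institutional policies".

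**The concern.** Scoring death as 6 is sensible. The difficulty is that whether a 12-month value exists then depends on vital status: it is certain for a known death and less than certain for a survivor. A weight model without vital status gives both groups the same averaged probability, so it cannot restore the balance between dead and living patients. The unweighted mixed model does not restore it either, because it predicts living non-responders from data that include the 6s.

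At stake is the proportion with good outcome on a primary endpoint. Because no deaths sit at month 0, a month-12 error passes into the month 0 to 12 change. If survivor retention differs between arms, which the contact and payment schedules make possible, the error need not cancel.

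**Working it through.** **Inputs.** The scoring, dichotomy, contrast and weight model are as stated above. The documents give no mRS rate, 12-month mortality, retention or completeness of death ascertainment, so there is no plan figure to reproduce. Assumed: mortality m of 5%, 8% or 10%; survivor retention r of 90% (ISPU) and 70% (CSC/PSC); g = 75% of survivors with mRS 0 to 2; no true arm difference.

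**1. Size when all deaths are known and living non-responders resemble responders.**
Observed good = (1−m)·r·g / [m + (1−m)·r]. True good = (1−m)·g.

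| m | True | r = 0.9 | r = 0.7 | Spurious difference |
|---|---|---|---|---|
| 5% | 71.25% | 0.64125/0.905 = 70.86% | 0.49875/0.715 = 69.76% | 1.1 |
| 8% | 69.0% | 0.621/0.908 = 68.4% | 0.483/0.724 = 66.7% | 1.7 |
| 10% | 67.5% | 0.6075/0.910 = 66.76% | 0.4725/0.730 = 64.73% | 2.0 |

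With equal retention the arm difference is unbiased, but each arm is too low by 0.4 points (m = 5%, r = 0.9) to 1.6 points (m = 10%, r = 0.8).

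**2. Why the SAP weights do not repair this.** Among patients with the same covariates, the fitted probability of an observed value is m + (1−m)·r for everyone. The weight is then constant and cancels, leaving the observed figures above. The probabilities that are needed are 1 for deaths and r for survivors, which give (1−m)·r·g/r ÷ [m + (1−m)] = (1−m)·g, the truth.

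A one-arm simulation (600,000 patients per scenario, one severity covariate, no site effect, about 30% of survivors poor) gave these errors in percent poor:

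| Method | 5% mortality, r = 0.9 / 0.8 / 0.7 | 10% mortality, r = 0.9 / 0.8 / 0.7 |
|---|---|---|
| SAP weights | +0.4 / +0.9 / +1.4 | +0.7 / +1.6 / +2.6 |
| Deaths coded as not observed in the weight model | +0.9 / +1.4 / +2.1 | +1.7 / +2.8 / +4.2 |
| Unweighted repeated-measures model | +0.2 to +0.7 | +0.4 to +1.9 |
| Deaths weight 1, response modelled in survivors | within 0.05 of 0 | within 0.05 of 0 |

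The unweighted repeated-measures model carries about half the closed-form error at 5% mortality and somewhat more than half at 10%. Putting the SAP weights into that model brought the error back to +0.4 to +1.6 and +0.7 to +2.6.

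**3. Direction depends on who the living non-responders are.** Let d be mortality and q and qn the poor rates in living responders and non-responders. Observed poor = [d + (1−d)·r·q] / [d + (1−d)·r]. True poor = d + (1−d)·[r·q + (1−r)·qn]. With d = 5%, r = 0.8 and q = 0.30, observed poor = 0.278/0.81 = 34.3%.
- qn = 0.30: truth 33.5%, error +0.82.
- qn = 0.343: error zero, with non-responders only 4.3 points worse than responders.
- qn = 0.40: truth 35.4%, error −1.08 (−1.45 at r = 0.7).

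**4. Direction depends on death ascertainment.** If only a share a of deaths is known, replace d by a·d in the observed formula. With qn = q = 0.30 and the same d and r, the error is +0.82 at a = 100%, +0.41 at 90%, zero at 80% (0.268/0.80 = 33.5%) and −0.42 at 70%.

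**5. The link to retention needs similar mortality.** At q = 0.30, d = 10% with r = 0.9 gives +0.69, which exceeds +0.51 for d = 3% with r = 0.8.

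**6. Scale.** Take 1,262 patients (Protocol Summary), 21 sites (SAP 1) assumed equal, 34% poor, and an assumed ICC of 0.01 to 0.05. Cluster size is 1,262/21 ≈ 60, so the design effect is 1.59 to 3.96. SE = √(2 × 0.34 × 0.66 / 631 × design effect) = 3.4 to 5.3 points for the 12-month difference.

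**7. Behaviour of candidate remedies (m = 8%, g = 75%).**
- *Unknown status treated as alive, deaths weight 1.* If deaths are captured no better than survivors (90% and 70%), known deaths are 7.2% and 5.6%. The estimates are 0.928 × 0.75 = 69.6% and 0.944 × 0.75 = 70.8%, a spurious 1.2 points favouring CSC/PSC.
- *Two steps: status known, then response among those known alive.* If vital status is known equally often for dead and living, both arms return 69.0%. If all deaths are known and 90% of survivors are known alive, with r = 0.7, the known-dead share is 0.08/0.908 = 8.8%. The estimate is 0.912 × 0.75 = 68.4%, against 66.7% with the SAP weights. If survivors are known alive only through an mRS, the two-step weights reduce to the SAP weights.

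**The case against.** The strongest objection concerns direction. A reader might infer that the plan over-counts poor outcomes and so favours ISPU. The documents do not support that. It needs random survivor non-response given the covariates, better capture of deaths than of survivors' responses, and similar mortality. Protocol section 9 itself expects survivors who cannot return because of morbid conditions. Deaths are assessed at visits, and a patient who also refuses telephone or virtual follow-up is not followed. With sparser surveillance in CSC/PSC, deaths could be missed more often there, which would offset the effect. This objection stands.

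The retention gap is also an assumption. The same telephone unit, the same outcome-collection rate and the same telephone or virtual fallback apply in both arms, and the protocol expects little additional missing data. At 90% versus 80% retention (3% to 10% mortality, 30% of survivors poor) the arm gap is only 0.3 to 0.8 points. This stands as a limit on size.

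A reader might also infer that the weighted mRS result automatically leads when the analyses differ. That sentence in SAP 3.1 is written for the six intermediate factors, and SAP 3.2 only asks for both analyses. Nor can one say that the plan as a whole leaves every living non-responder missing. The protocol's floor score covers survivors who cannot return, but it appears in the SIS paragraph and is not carried into SAP 3.2.

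What survives is narrower. The weights fail under their own assumption that non-response depends only on the covariates, and an unknown offsetting bias is no reason to keep them.

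**Conclusion.** The concern holds in conditional form. The scoring asymmetry is in the SAP text, and weights without vital status do not correct it. Under random survivor non-response given covariates, well-captured deaths and similar mortality, the SAP weights leave about 0.4 to 2.7 points of excess poor outcome per arm (5% to 10% mortality, 90% to 70% retention). The spurious arm difference at 90% versus 70% retention is 1.1 to 2.0 points in closed form and less in the unweighted repeated-measures model. All of this lies below a likely standard error of 3.4 to 5.3 points. Outside those conditions the net direction is unknown, and the arm with worse retention may have the larger under-count. The point merits correction because it is a systematic error in a primary outcome with an inexpensive remedy. It does not show that the trial is biased toward either arm.

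**What to change.** For the weighted mRS analysis in SAP 3.2:

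1. Model the probability that 12-month vital status is known, in all patients.
2. Model the probability of an observed mRS among those known alive at 12 months.
3. Give known deaths the inverse of the step 1 probability, and living responders the inverse of the product of the two.

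This helps to the extent that vital status is known for patients without an mRS. The separate site mortality surveillance and medical records should supply much of that.

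Add two sensitivity analyses. In the first, treat unknown vital status as alive (known deaths weight 1, response modelled in all others). In the second, vary the poor-outcome rate assumed for living non-responders. The second is needed because correct handling of deaths does not address sicker non-responders: with deaths at weight 1, errors of −1.0 to −4.2 points remained in the scenarios tried.

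Also state whether the weighted-result precedence rule applies to the mRS, and reconcile SAP 3.2 with the protocol's floor score for survivors who cannot return. Report by arm the numbers dead, alive with mRS, alive without mRS and of unknown vital status.

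The cost is SAP wording, slightly more programming and somewhat more variable weights. No new data collection is required.

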## **1. Introduction**

C3FIT is a cluster -randomized clinical trial randomizing 24 sites (21 of which provided data and will be included) to assess the effectiveness, defined at 12-months post-stroke discharge, of post-stroke care delivered using the Joint Commission (JC)-certified Comprehensive or Primary Care (CSC/PSC) model compared to an integrated, coordinated, technology-enabled Integrated Stroke Practice Unit (ISPU) model (that includes CSC/PSC care). The trial has two primary outcomes, the modified Rankin score (mRS) and the Stroke Impact Scale (SIS), both assessed at baseline (for SIS, only in approximately 50% of the participants), and at 3, 6 and 12 months. Any beneficial treatment effect of the ISPU approach on the mRS and SIS is presumed to be through a beneficial effect on “intermediate” factors, specifically better control of: 1) systolic blood pressure (SBP) to levels below 130 mmHg, 2) LDL levels to levels below 70 mg/dL, 3) HbA1c to levels below 7%, 4) smoking cessation, 5) adherence to AHA diet guidelines by following a Mediterranean-type or DASH diet, and 6) adherence to AHA exercise guidelines by a usual exercise level of moderate or above. Each of these intermediate factors will be assessed among those failing to be in control at hospital discharge (i.e., for SBP, among those with discharge SBP $\geq$ 130 mmHg; for LDL, among those with discharge LDL levels above 70 mg/dL, etc.). Because of this presumed pathway for potential effects, the assessment of treatment effects on these six intermediate factors is considered an integral part of the assessment of primary outcomes. Because the cluster-randomization may fail to balance the treatment groups on key factors potentially affecting outcome, treatment differences will be assessed after a series of incremental models, first in a crude model with no adjustment, then with adjustment for measures of stroke severity, then with further adjustment for demographic factors, and then with further adjustment for major cardiovascular risk factors. Treatment differences for both the two primary outcome variables and the six intermediate factors will be assessed using a mixed model approach including the assessments at baseline, 3 months, 6 months and 12 months.

Beyond the intermediate factors above, the study also has secondary outcomes including mortality, recurrent stroke, rehospitalization, time at home, depression, caregiver strain, and perceived support.

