## **2. Definitions and classification of covariates**

The covariates used in the incremental models include measures of stroke severity, demographic factors, and traditional cerebrovascular risk factors.

- Measures of stroke severity
  - Discharge location, classified as discharged home vs. not home (skilled nursing, rehabilitation center, etc.).

- Discharge mRS, categorized as 0, 1, 2, 3 or 4 or more (noting relatively few patients with discharge mRS of 5).
- Discharge NIH Stroke Scale (NIHSS), categorized into approximate quartiles of 0, 1, 2-4 or 5+
- Stroke subtype (hemorrhage vs. infarction)
- Demographic factors
  - Age, considered as a continuous factor
  - Male sex
  - Race/Ethnicity, categorized as non-Hispanic white (NHW) versus not NHW (including both other races and Hispanic participants)
  - A summary neighborhood index of socio-economic status (nSES) based on previously published methods, including six variables representing wealth/income, education and occupation: (1) log of median household income, (2) log of median value of owner-occupied housing units, (3) proportion of households receiving interest, dividend, or net rental income, (4) proportion of adults aged  $\geq 25$  years with a high school diploma, (5) proportion of adults aged  $\geq 25$  years with college degree, and (6) proportion of people employed in executive, managerial or professional occupations.
- Baseline cerebrovascular risk factors
  - Cigarette smoking, categorized as current vs. non-current (past or never)
  - Hypertension as a dichotomous variable
  - Dyslipidemia as a dichotomous variable
  - Diabetes as a dichotomous variable
  - Atrial fibrillation or irregular heartbeat as a dichotomous variable
  - Sedentary activity (defined as a score of 0-No Physical Activity or 1-Sedentary or sitting most of the time)

Because the mixed models will include baseline assessment of the outcome variable (i.e., outcomes include measures at times 0, 3, 6, and 12 months), covariates directly related to the outcome being assessed will be excluded from the model. That is, variables will not be used as both an outcome and as a predictor in the same model. For example, discharge mRS will not be included in the models predicting treatment differences in mRS, and baseline hypertension will not be included in models assessing treatment differences in SBP. Rather, changes from baseline to the 3, 6 and 12-month visits will be assessed using contrast statements.

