### **3.3. Stroke Impact Scale (SIS)**

The SIS is a continuous outcome variable with a range from 0 to 100 which will be analyzed identically to continuous intervening factors measured at 4 timepoints (including the analysis with inverse probability weighting). We do note that: 1) after approximately half the patients were recruited, a decision was made to not collect SIS at baseline; however, it is quite reasonable to assume that this decision will give rise to data missing at random and the missingness will be addressed by the mixed models, and 2) the baseline SIS collected were the “long form” of the questionnaire (96 items); however, the 16 items in the short form used at 3, 6 and 12 months are a subset of the long form, and these items will be extracted and scored identically with the follow-up assessments. The analysis of SIS will employ analysis for a continuous factor, but will follow the modeling approach described above for mRS, specifically reporting treatment differences in mean SIS rather than treatment differences in the proportion with good mRS outcome (primary outcome as treatment difference in the change in mean SIS between baseline and 12 months, 4-level incremental models, with/without inverse probability weighting, assessment of effect modifiers, etc.).

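### The SAP specifies no covariate-by-visit terms; with main effects only, its four-step adjustment leaves imbalance in predictors of recovery in the primary change contrasts

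*SAP*

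**What the plan says.** SAP section 1 gives the reason for adjusting: "Because the cluster-randomization may fail to balance the treatment groups on key factors potentially affecting outcome". Four models answer this: a crude one, then severity, demographics and risk factors added in turn. Section 2 lists the covariates, all measured once. It places month 0 among the modelled outcomes and states that "changes from baseline to the 3, 6 and 12-month visits will be assessed using contrast statements".

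The primary contrast for mRS (3.2) is a change: "The primary outcome will be treatment differences in the change in the proportion with good outcomes between months 0 and 12". SIS (3.3) follows: "primary outcome as treatment difference in the change in mean SIS between baseline and 12 months, 4-level incremental models". Section 3.2 carries the adjustment over to the change: "These differences will be estimated with the same 4-level incremental adjustments, and with both unadjusted and inverse-probability weighted adjustment". The supplemental all-patient analysis of the intermediate factors in 3.1 also focuses on change from month 0 to month 12.

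Arm differences are also "reported with the p-value for treatment differences at each time point", so the month-0 arm means are estimated freely and not constrained to be equal. No section states or excludes a covariate-by-visit term.

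**The concern.** A baseline covariate with one coefficient moves a patient's expected month-0 and month-12 values by the same amount. When the primary quantity is the difference between those two values, that coefficient has nothing to act on. The adjustment promised against cluster imbalance would then do no work on the contrast that decides the trial. Similar primary results from four models could be read as evidence that confounding was examined and found absent.

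Unequal effects at the two times are plausible here. Discharge NIHSS is measured at the month-0 time point, and its effect need not be the same a year later. Nobody can score 6 on the mRS at month 0, but deaths score 6 at follow-up (SAP 3.2), so a predictor of death can act through death at month 12 and not at discharge. Protocol section 9 itself names age and stroke severity as strongly related to outcome.

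**Working it through.** **Inputs from the documents.** 21 sites analysed (SAP 1); 1,262 patients (protocol Summary); baseline SIS in about half of participants (SAP 1 and 3.3); SIS SD about 8, ICC 0.05, target 2.7 points at 80% power (protocol 9A). **Assumed, because the documents give no values:** the arm imbalance, the covariate slopes, an ICC of 0.05 for the covariate, and two-sided alpha 0.05.

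**1. The protocol's yardstick.** For 18 sites of 100, SE = 8 × √(2 × (1 + 99 × 0.05)/900) = 0.92. A non-central t with 16 df gives detectable differences of 2.75 (80% power) and 3.18 (90%), against the stated 2.7 and 3.2. The figure reproduces and serves below only as a scale.

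**2. Algebra.** With main effects, E[Y_t] = a_t + d_t·trt + g·X. Then E[Y_12 − Y_0] = (a_12 − a_0) + (d_12 − d_0)·trt, which contains no g. If the true covariate effect is g_t and the arms differ by Δ in mean X, the crude and the main-effects contrast both carry a bias of

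Δ × (g_12 − g_0).

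If g_12 = g_0, this is zero even in the crude model. Replacing g·X by g_t·X (covariate × visit) removes it.

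**3. Simulation.** No true treatment effect; Δ = 0.3 SD in one covariate. In the shrinking case (150 data sets of 1,262, patient intercept) the SIS slope goes from -10 per SD at discharge to -5 at month 12. In the growing and constant cases (60 data sets of 1,260) SIS has patient and site intercepts over 21 sites; mRS is a logistic model with a patient intercept and no site effect.

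| Change contrast, month 0 to 12 | Crude | Main effects | Covariate × visit |
|---|---|---|---|
| SIS, shrinking, complete data | +1.47 | +1.47 | -0.02 |
| SIS, shrinking, half of month 0 and 15% of later visits missing | +1.60 | +1.60 | +0.10 |
| SIS, growing, complete data | -1.46 | -1.46 | +0.10 |
| SIS, growing, half of month 0 missing plus dropout | -1.23 | -1.28 | +0.09 |
| SIS, constant effect, complete data | +0.07 | +0.07 | +0.06 |
| mRS, growing, log-odds | -0.164 | -0.162 | -0.009 |
| mRS, growing, percentage points at covariate mean | -2.5 | -3.7 | -0.3 |
| mRS, growing, percentage points, standardised | -2.3 | -2.6 | -0.2 |

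With complete SIS data, crude and main-effects estimates agree in every data set to about 1e-12. In the growing case with missing data they differ by up to 0.21 to 0.36 points in a single data set, but by only 0.02 to 0.05 on average, and the bias stays.

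The month-12 level behaves differently. In the growing case with complete data, main-effect adjustment takes the SIS difference from -2.93 to -0.57 and the mRS log-odds difference from -0.34 to -0.06.

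**4. Size.** Chance SE of an imbalance: 1,262/21 = 60.1 patients per site, and √(4 × (1 + 59.1 × 0.05)/1,262) = 0.11 SD. So 0.3 SD is about 2.7 SEs.

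- Slopes that fit SD 8 (assumed severity correlations 0.6 at discharge and 0.3 at month 12): 0.6 × 8 = 4.8 and 0.3 × 8 = 2.4, so g_12 − g_0 = 2.4. Bias: 0.11 × 2.4 = 0.26; 0.3 × 2.4 = 0.72.
- Slopes -10 and -5: g_12 − g_0 = 5. Bias: 0.11 × 5 = 0.55; 0.3 × 5 = 1.5.

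**The case against.** - **The main-effects model is inferred.** The SAP neither states nor rules out visit interactions. This stands, and the point is worded conditionally. But adjusting for a covariate ordinarily means a main effect, and default code would fit one. If interactions were intended, the primary model still needs to say so.
- **A reader might infer that the four models must return the same primary result.** The documents do not support that. Identity is exact only for a linear model with complete data. About half of baseline SIS is missing, and mRS is modelled through a link but judged as a change in proportion, so estimates will move. In the growing case the mRS proportion contrast moved away from the true zero.
- **A reader might infer that any prognostic imbalance stays.** It does not. A constant effect over visits cancels on the model scale. For mRS with a constant log-odds effect, main-effect adjustment brought the proportion contrast at the covariate mean from +1.65 to +0.3 points, so there it suffices.
- **Other outputs do respond.** Per-visit differences, including month 12, change under main-effect adjustment, so an attentive reader would see some movement. The restricted primary analysis of the intermediate factors in 3.1 uses month-12 levels without a month-0 outcome and is unaffected. Neither fact repairs the contrasts that 3.2 and 3.3 name as primary.
- **Inverse-probability weighting might be thought to help.** It models the chance that month 12 is observed (SAP 3.1). It addresses missingness, not arm imbalance.

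**Conclusion.** The point holds as a specification gap with a real consequence. On the ordinary main-effects reading, the four-step adjustment does not do the job section 1 gives it for the change contrasts in 3.2, 3.3 and the supplemental part of 3.1. Imbalance in predictors of recovery stays in the adjusted primary effect.

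The cancellation for SIS with complete data is algebra and needs no assumed numbers. The size does. A plausible range is about 0.3 to 0.7 SIS points (roughly 10% to 27% of the 2.7-point target) for an imbalance of 0.11 to 0.3 SD with slopes that fit SD 8, and 0.55 to 1.5 points with slopes of -10 and -5.

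A reader might set 1.5 against 2.7 and call it more than half the target. That is not supported: a slope of -10 per SD alone implies an SIS SD above 10, while the 2.7 rests on SD 8, and 0.3 SD is a tail imbalance at about 2.7 chance SEs. Because the gap affects both primary outcomes, it should be closed before analysis.

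**What to change.** In SAP sections 2, 3.1 (supplemental analysis), 3.2 and 3.3, state that in every model with four time points each adjustment covariate enters with its interaction with visit. Report from that model the adjusted arm difference in change from month 0 to month 12.

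Cost: one sentence in each place and extra model terms. For SIS the section 2 list gives 9 severity, 4 demographic and 6 risk-factor parameters, 19 in all, so 19 × 3 = 57 interaction parameters against roughly 4,000 records. If a binary model fails to converge, keep the interactions for severity and age first, and write that order into the SAP.
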